### Attachment 3. Protocol GWBQ

## American Diabetes Association: Diagnosis of Diabetes Mellitus\*

---

1. Symptoms of diabetes plus casual plasma glucose concentration greater than or equal to 200 mg/dl (11.1 mmol/L).

Casual is defined as any time of day without regard to time since last meal. The classic symptoms of diabetes include polyuria, polydipsia, and unexplained weight loss.

OR

2. Fasting plasma glucose greater than or equal to 126 mg/dl (7mmol/L).

Fasting is defined as no caloric intake for at least 8 hours.

OR

3. 2-h Plasma glucose greater than or equal to 200 mg/dl (11.1 mmol/L) during an OGTT.

The test should be performed as described by the World Health Organization, using a glucose load containing the equivalent of 75g anhydrous glucose dissolved in water.

NOTE:

In the absence of unequivocal hyperglycemia, in order to make a diagnosis of diabetes mellitus, these criteria should be confirmed by repeat testing on a different day.

The OGTT is not recommended for routine clinical use, but may be required in the evaluations of patients with impaired fasting glucose or when diabetes is still suspected despite a normal FPG.

The use of the hemoglobin A1c (A1C) for the diagnosis of diabetes is *not* recommended at this time.

\*[ADA's Clinical Practice Recommendations 2007](#)

---

## **Attachment 4. Protocol GWBQ Lifestyle Modification Program**

---

A simplified lifestyle modification program (LMP) will be recommended for all patients participating in study GWBQ. The LMP consists of a diet and exercise component suggested to be followed throughout the duration of the study. This program will address the dietary and physical activity needs of the individual. A qualified person (i.e.) Registered Dietitian (RD) or Certified Diabetes Educator (CDE) will meet with the patient and parent or guardian at each scheduled clinic visit. The LMP will be reinforced at each visit.

The study LMP for sites located in the U.S. will be based on the “MyPlate Plan”, a program designed by the United States Department of Agriculture and available to the public at [www.ChooseMyPlate.gov](http://www.ChooseMyPlate.gov). The qualified person at each site will enter each patient’s age, gender, weight and height into the SuperTracker program calculator. The program will calculate the total daily calories recommended to be consumed to promote at least minimal weight loss and to meet growth needs. The MyPlate Plan will also be used to calculate the number of daily meal servings from each food group in the plan.

The qualified person can individualize the MyPlate Plan using clinical judgment to promote compliance with the meal plans and physical activity throughout the study. At each clinic visit, individualized tools can be given to the patient with a copy retained by the qualified person.

For countries other than the US, the study LMP will be based on the “MyPlate Plan” or other locally applicable plan.

### **Visit 2 (Beginning of the placebo lead-in period)**

The qualified person will meet with the patient and parent or guardian beginning at Visit 2 of the study. The qualified person will introduce and review the MyPlate with the patient and parent/guardian, explaining the recommended number of calories, food groups, portion sizes, and individualizing the plan to aid patient compliance. The patient will be given at least three food and exercise worksheets. The patient will be instructed to complete a minimum of one of the worksheets with at least two weekdays and one weekend day of food consumption and exercise. The patient will be instructed to complete the worksheet prior to Visit 3 and bring the worksheet with them to the next clinic visit.

The qualified person will instruct the patients on the importance of a minimum of 60 minutes of daily exercise (walking, jogging, biking, hiking, sport activity, etc) and limiting sedentary activities (watching TV, video games) to one hour or less daily.

### **Visit 3 (Randomization) through Visit 10**

The qualified person will meet with the patient and parent/guardian to collect and review the food and exercise worksheets, during clinic visits. The qualified person will evaluate adherence to the LMP and address any areas of concern. The patient’s weight will be noted at each clinic

visit to help assess diet and exercise compliance. The qualified person will re-instruct patient on problem areas, as appropriate. The qualified person will reinforce positive changes and encourage the patient to adhere to both the diet and exercise recommendations. The patient will be given at least three food and exercise worksheets. The patient will be instructed to complete a minimum of two of the worksheets with at least two weekdays and one weekend day of food consumption and exercise. The patient will be instructed to complete the worksheets prior to the clinic visit and bring the worksheets with them to the next clinic visit. During the phone visits the patient may speak with the qualified person on the LMP if requested.

**Visit 11 (End of study treatment)**

The qualified person will meet with the patient and parent/guardian and collect the food and exercise worksheets. The patient should be encouraged to maintain a healthy lifestyle after the patient ends study treatment and enters the safety follow-up period, at the discretion of the investigator.

Footnote: Failure to return food and exercise worksheets will not, at any time, be considered a protocol violation.

---

## Attachment 5. Protocol GWBQ Estimated Glomerular Filtration Rate

---

Note: The central laboratory applies the formula and reports the value in its calculated form.

### Standard Schwartz Formula for Estimated Glomerular Filtration Rate (GFR)a

*For glomerular filtration rate in mL/min/1.73 m^2*

$$\text{GFR} = k^b \times \text{height(cm)}/\text{serum creatinine (mg/dL)}$$

a [Schwartz GJ et al, 1976](#); [Schwartz et al, 1984](#); [Schwartz et al, 1985](#).

b  $k = 0.55$  in male children aged 2 -12 years and all female children and adolescents up to age 17 years ;  $k = 0.65$  for adolescent males aged 13-17 years.

### Modification of Diet in Renal Disease (MDRD) Formula for Estimated Glomerular Filtration Rate (GFR) in Adults

- $\text{GFR (mL/min/1.73 m}^2) = 175 \times (\text{serum creatinine})^{-1.154} \times (\text{Age})^{-0.203} \times (0.742 \text{ if female}) \times (1.212 \text{ if African American})$

### CKD-EPI Formula for Estimated Glomerular Filtration Rate (GFR) in Adults

$$\text{GFR (mL/min/1.73 m}^2) = 141 \times \min(\text{Scr}/k, 1)^a \times \max(\text{Scr}/k, 1)^{-1.209} \times 0.993^{\text{Age}} \times [1.018 \text{ if female}] \times 1.159 \text{ if black}]$$

**Amendment (a) to Protocol Addendum  
H8O-MC-GWBQ(3)  
Safety and Efficacy of Exenatide as Monotherapy and  
Adjunctive Therapy to Oral Antidiabetic Agents in  
Adolescents with Type 2 Diabetes**

## Rationale for Addendum

To provide a thorough quantification of the pharmacokinetic (PK) disposition of exenatide in adolescents and allow assessment of safety endpoints relative to maximum plasma exenatide concentrations observed in adolescent patients, additional PK samples will be collected. Optimal design analysis has demonstrated that data from a limited number of subjects in the current study, combined with existing PK data from Amylin Study 2993-124, will provide a robust characterization of exenatide PK in adolescents. At least 36 subjects (12 from each treatment arm) enrolled in Study H8O-MC-GWBQ will be incorporated into the population PK analyses.

- Group A: PK samples will be collected once at Visit 3 at 2 hours post dose. This group will consist of at least 24 subjects, evenly divided among treatment groups (placebo twice daily: 8 subjects, exenatide 5 mcg twice daily: 8 subjects, and exenatide 10 mcg twice daily: 8 subjects). This is to allow for the assessment of  $C_{max}$  in the adolescent population.
- Group B: PK samples will be collected twice during Visit 3: once at 30 minutes post dose and once at 4 hours post dose. This group will consist of at least 12 subjects, evenly divided among treatment groups (placebo twice daily: 4 subjects, exenatide 5 mcg twice daily: 4 subjects, and exenatide 10 mcg twice daily: 4 subjects).

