For approximately the first 4 weeks of therapy (until visit 5), patients assigned to both exenatide 5 µg, 10 µg and both placebo groups will inject, either exenatide 5 µg or equivalent volume of placebo, within 60 minutes before the morning and evening meals (or the two main meals of the day, approximately 6 hours or more apart). After visit 5, patients assigned to exenatide 10 µg and its matching placebo will begin injecting 10 µg twice daily.

In the week prior to Visits 3 and 11, patients will be asked to perform pre- and 2-hour postprandial blood glucose measurements at the 2 main meals of the day on 3 separate days. These glucose measurements should be recorded along with study drug dose in the patient diaries. In addition to these requested glucose measurements, patients will be encouraged to measure daily fasting glucose values at home. The diaries are considered source documents and are to be returned to the investigator at the clinic visit. If a patient fails to perform any of the aforementioned measurements, this will not constitute a protocol violation.

Also occurring at Visits 3 and 11, will be the collection of CEA and calcitonin.

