## Protocol Additions

### Laboratory Tests

#### ***Pharmacokinetic Sampling***

Additional PK sampling will be performed at Visit 3 in a subset of subjects. At least 36 subjects, from the US, will be chosen from select sites and randomly assigned to 1 of 2 groups:

- Group A: PK samples will be collected once at Visit 3 at 2 hours post dose. This group will consist of at least 24 subjects, evenly divided among treatment groups (placebo twice daily: 8 subjects, exenatide 5 mcg twice daily: 8 subjects, and exenatide 10 mcg twice daily: 8 subjects).
- Group B: PK samples will be collected twice during Visit 3: once at 30 minutes post dose and once at 4 hours post dose. This group will consist of at least 12 subjects, evenly divided among treatment groups (placebo twice daily: 4 subjects, exenatide 5 mcg twice daily: 4 subjects, and exenatide 10 mcg twice daily: 4 subjects).

Dosing of subjects on the PK addendum at Visit 3 will be altered from that in the main protocol. Subjects will administer their first dose of the assigned therapy at Visit 3 (approximately 15 min before receipt of first meal at the clinic)

Subjects participating in the PK addendum are not to take their evening dose on the day of Visit 3.

Drug concentration information that would unblind the study will not be reported to investigative sites or blinded personnel until the study has been unblinded.

Bioanalytical samples collected to measure investigational product concentration will be retained for a maximum of 2 years following last patient visit for the study.

At the visits and times specified in the Study Schedule, venous blood samples ([Attachment 1](#)) will be collected ([Attachment 2](#)). Blood samples will be used to determine the plasma concentrations of LY2148568. The actual date and time (24-hour clock time) of each sampling will be recorded.

A maximum of 2 samples may be drawn at additional time points during the study if warranted and agreed upon between both the investigator and sponsor. Instructions for the collection and handling of blood samples will be provided by the sponsor.

---

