### Study Schedule for PK Samples, Protocol Addendum H8O-MC-GWBQ(3)

CRF Visit No.:	V3
Time relative to V3 (baseline) - days	0
Procedure	
PK informed consent signed	X
Venous blood PK samples a,b	X

a PK samples must be collected only after the subject signs the PK informed consent document.

- b Group A: PK samples will be collected once at Visit 3 at 2 hours post dose. This group will consist of 24 subjects, evenly divided among treatment groups (placebo twice daily: 8 subjects, exenatide 5 mcg twice daily: 8 subjects, and exenatide 10 mcg twice daily: 8 subjects).
- Group B: PK samples will be collected twice during Visit 3: once at 30 minutes post dose and once at 4 hours post dose. This group will consist of 12 subjects, evenly divided among treatment groups (placebo twice daily: 4 subjects, exenatide 5 mcg twice daily: 4 subjects, and exenatide 10 mcg twice daily: 4 subjects)..

---

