### Protocol H8O-MC-GWBQ Sampling Summary

Purpose	Sample Type	Maximum Amount per Sample	Maximum Number Samples	Maximum Total Amount
Drug concentration: Group A: PK samples	Blood	4 mL	1 +2 additional samples if warranted	12 mL
Drug Concentration Group B: PK samples	Blood	4 mL	2+2 additional samples if warranted	16mL

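### Does it matter that every scheduled Addendum 3 PK sample follows the first 5 µg-step injection, when one stated aim is to relate safety to maximum exenatide concentration?

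*Protocol*

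**What the plan says.** The Rationale of Protocol Addendum 3 gives two reasons for the PK samples: to quantify exenatide disposition in adolescents, and to "allow assessment of safety endpoints relative to maximum plasma exenatide concentrations observed in adolescent patients". Of the Group A sample at 2 hours it says "This is to allow for the assessment of" Cmax. On numbers: "At least 36 subjects (12 from each treatment arm) enrolled in Study H8O-MC-GWBQ will be incorporated into the population PK analyses".

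The timing is fixed under Pharmacokinetic Sampling and in the Addendum's Attachment 1. "Subjects will administer their first dose of the assigned therapy at Visit 3", shortly before a meal at the clinic. Group A is then sampled once, at 2 hours. For Group B, "PK samples will be collected twice during Visit 3: once at 30 minutes post dose and once at 4 hours post dose". There is also a discretionary clause: "A maximum of 2 samples may be drawn at additional time points during the study if warranted" and agreed between investigator and sponsor. The sampling summary in Attachment 2 allows for it, for example "1 +2 additional samples if warranted" in Group A.

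Protocol 6.1.3 sets the dose at that time: "For approximately the first 4 weeks of therapy (until visit 5), patients assigned to both exenatide" dose levels inject the 5 µg step, and the 10 µg arm moves up only after Visit 5.

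In the SAP, PK is an exploratory objective (1.1.3). The PK analysis set (2.1.7) is used for a listing, and 4.2.6 plans a listing only. The amendment history and Section 6 both record this restriction, and Section 6 gives lack of data as the reason.

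**The concern.** An exposure-safety assessment needs concentrations from the dose that patients were taking when safety was observed. Here the safety endpoints run over the whole treatment period (SAP 3.4), while the scheduled concentrations all come from the first day, at a dose step that the 10 µg arm leaves at Week 4. The two exenatide arms therefore contribute no dose contrast to the measured concentrations, and any peak value at 10 µg would be extrapolated. Protocol 8.4 describes the earlier adolescent study, which the Addendum intends to combine with these data, as using single doses of 2.5 and 5 µg. It reports rough dose proportionality only in subjects with quantifiable levels.

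If someone later set adverse events over 28 weeks against these concentrations, a flat relation could be misread as reassurance. There is also a question of justification: adolescents give additional blood partly for a purpose that the schedule does not serve at the higher step. The SAP then contains neither that assessment nor the population PK analysis named in the Addendum.

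**Working it through.** **Reproducing the Addendum's own figures.**
- Patients: Group A 3 × 8 = 24; Group B 3 × 4 = 12; total 36, or 8 + 4 = 12 per arm. This agrees with the Addendum.
- Maximum blood volume: Group A (1 + 2) × 4 mL = 12 mL; Group B (2 + 2) × 4 mL = 16 mL. Both agree with Attachment 2.

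**Scheduled samples at the planned minimum.**
- Per arm: 8 × 1 + 4 × 2 = 16. All arms: 3 × 16 = 48. Exenatide arms: 2 × 16 = 32.
- Scheduled samples after a 10 µg injection: 0 of the 16 in the 10 µg arm.
- Time at the 10 µg step: 28 − 4 = 24 weeks, and 24/28 = 86%.
- Optional samples in the 10 µg arm: between 0 and 12 × 2 = 24. None has a planned time.

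So the statement is right for scheduled samples. It would be too strong to say that the design rules out measurement at 10 µg.

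**Is there a usable size for the loss?** Suppose exposure doubles from 5 to 10 µg and the between-patient CV is 30% to 60%. Both are assumptions; the CV is not in the documents. With two equal arms, the dose contrast adds (ln 2)²/4 = 0.120 to the variance of log Cmax. Within-arm variance is ln(1 + CV²), which is 0.086 at 30% and 0.307 at 60%. The dose share is then 0.120/(0.120 + 0.086) = 58% to 0.120/(0.120 + 0.307) = 28%.

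These shares do not measure lost information. Assigned dose and schedule are known. If proportionality holds, the factor of 2 can be applied and the contrast recovered; if it fails, 0.120 is the wrong number. Weeks without a scheduled sample are no better as a measure, because the 5 µg arm also has none after Visit 3.

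**What in the SAP uses the concentrations?**

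| Item | SAP section | Use of PK data |
|---|---|---|
| Primary and secondary efficacy | 4.2.4 | none |
| Safety tables by arm | 4.2.5 | none |
| PK | 2.1.7, 4.2.6 | listing |
| Declared change from protocol | 6 | listing only, lack of data |

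No planned display sets safety against concentration, so the feared misreading has no planned output in which to occur. Protocol 11.2.1 asks that changes to non-primary analyses be described and justified in the SAP, and Section 6 does this for the PK data.

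**What would a scheduled sample at 10 µg have cost?** One added sample at Visit 7 or 9 fits the volume limits: (1 + 1) × 4 = 8 of 12 mL in Group A and (2 + 1) × 4 = 12 of 16 mL in Group B. Volume is not the main cost. The study schedule tells patients not to inject before coming to the site, and Protocol 8.5 ties the injection to the hour before a main meal. A 2-hour sample would therefore need an injection and a meal at the clinic, a stay of about 2 hours and another timed draw, in at least 36 patients across all arms to protect the blind.

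**The case for a change.** The strongest case for a change is that the stated purpose and the schedule do not fit. Protocol 8.4 already regards the pharmacokinetics of a single 5 µg dose in adolescents as well described, yet the Addendum schedules that condition again and leaves the higher step unmeasured. Optional samples with no planned time do not make the purpose achievable by design. Lack of data, the reason in SAP Section 6, is not the whole explanation, since more patients on the same schedule would still give no scheduled sample at 10 µg. Section 6 names neither the exposure-safety aim nor the population PK analysis. A listing by treatment received could also show a 10 µg label beside a concentration drawn on the 5 µg step.

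The facts in this argument stand; the need for a change does not follow.
- The Addendum speaks of maximum concentrations observed in adolescents. It does not promise them at 10 µg or over 28 weeks. First-dose levels also have some bearing on safety, since Protocol 4.1 notes that nausea is more frequent when therapy starts.
- The intended analysis was model-based, pooled with another study and supported by an optimal design analysis. None of this is shown, and a separate population PK plan may exist.
- All scheduled samples come from Visit 3, so a reader of the listing who has the protocol knows the dose step.
- Naming the dropped aim in Section 6 would improve disclosure, but no number in the report would change. The same holds for the cross-reference in 4.2.6, which points to 2.1.6 (the safety follow-up set) when the PK set is 2.1.7.

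**Conclusion.** The observation is accurate when limited to scheduled samples: 0 of 16 in the 10 µg arm follow a 10 µg injection, against 24 of 28 planned weeks at that step. Its consequence is confined to an exploratory objective for which the SAP already plans nothing beyond a listing, so no estimate, test or safety table would come out differently.

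The only alteration with substance, a scheduled sample after the step-up, belonged to the design stage. There it was a trade-off between better exposure data and an added in-clinic procedure for minors, and the sponsor's choice is defensible. By the SAP of April 2020 the decision to stop recruitment had been taken, with 122 patients randomized (SAP 1.3), so little could be gained by revisiting it. What is left is a disclosure gap and a wrong section number, both of which an analyst handles without an amendment.

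This conclusion assumes that concentrations are only listed, as SAP 4.2.6 and 6 state. If anyone later relates safety to these concentrations, the Visit 3 values must be read as 5 µg-step exposure in both exenatide arms, and any 10 µg value as extrapolated.

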## Protocol Additions

### Laboratory Tests

#### ***Pharmacokinetic Sampling***

Additional PK sampling will be performed at Visit 3 in a subset of subjects. At least 36 subjects, from the US, will be chosen from select sites and randomly assigned to 1 of 2 groups:

- Group A: PK samples will be collected once at Visit 3 at 2 hours post dose. This group will consist of at least 24 subjects, evenly divided among treatment groups (placebo twice daily: 8 subjects, exenatide 5 mcg twice daily: 8 subjects, and exenatide 10 mcg twice daily: 8 subjects).
- Group B: PK samples will be collected twice during Visit 3: once at 30 minutes post dose and once at 4 hours post dose. This group will consist of at least 12 subjects, evenly divided among treatment groups (placebo twice daily: 4 subjects, exenatide 5 mcg twice daily: 4 subjects, and exenatide 10 mcg twice daily: 4 subjects).

Dosing of subjects on the PK addendum at Visit 3 will be altered from that in the main protocol. Subjects will administer their first dose of the assigned therapy at Visit 3 (approximately 15 min before receipt of first meal at the clinic)

Subjects participating in the PK addendum are not to take their evening dose on the day of Visit 3.

Drug concentration information that would unblind the study will not be reported to investigative sites or blinded personnel until the study has been unblinded.

Bioanalytical samples collected to measure investigational product concentration will be retained for a maximum of 2 years following last patient visit for the study.

At the visits and times specified in the Study Schedule, venous blood samples ([Attachment 1](#)) will be collected ([Attachment 2](#)). Blood samples will be used to determine the plasma concentrations of LY2148568. The actual date and time (24-hour clock time) of each sampling will be recorded.

A maximum of 2 samples may be drawn at additional time points during the study if warranted and agreed upon between both the investigator and sponsor. Instructions for the collection and handling of blood samples will be provided by the sponsor.

---

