2.1.5 Safety analysis set

The Safety analysis set consists of all patients who received at least 1 dose of randomized study medication.

Patients will be analyzed and presented in accordance to the actual treatment received, regardless of planned treatment assignment. If a patient receives at least one dose of exenatide treatment during the assessment period, they will be analyzed and presented in accordance with the actual exenatide treatment received no matter what arm they were randomized to. If a patient randomized to the placebo arm receives exenatide at doses of both 5 µg twice daily and 10 µg twice daily, they will be analyzed and presented in the 10 µg twice daily treatment group.

This set will be used for listings and summaries of safety data during the treatment period.

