2.1.6 Safety follow-up analysis set

The safety follow-up (SFU) analysis set consists of all patients who have at least 1 safety follow-up period assessment Visit 801 (6 months after Week 28/ED) to Visit 806 (3 years after Week 28/ED).

This set will be used for listings and summaries of safety data during the safety follow-up period.

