2.1.7 Pharmacokinetic (PK) analysis set

The PK analysis set will consist of all patients who receive at least 1 dose of EBID, for whom at least 1 evaluable post-dose PK concentration assessment is available, and do not deviate from the clinical study protocol (CSP) in ways that would significantly affect the PK analyses, as determined at the final protocol deviations meeting prior to unblinding of this study. Patients will be presented in accordance to the actual treatment received.

This set will be used for listing of PK data.

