4.1.1 Statistical notations and presentations

Although patients randomly assigned to placebo will be assigned to take the volume equivalent to 5 µg exenatide twice daily or to take the volume equivalent to 10 µg exenatide twice daily, all patients assigned to placebo will be combined into 1 group for analysis purposes. Descriptive summaries will present treatment groups separately, as follows:

5 µg EBID	10 µg EBID	Total EBID	Placebo	Total
EBID Exenatide twice daily				

Total EBID is the pool of the 10 µg and 5 µg EBID doses. Total (over all treatments) will not be included in efficacy and safety endpoint outputs.

Summaries including data from the safety follow-up period will be presented by the actual treatment group during the randomized period.

All efficacy and safety variables will be summarized using descriptive statistics as appropriate. Continuous variables will be summarized by descriptive statistics including n (number of patients with available data), arithmetic mean, standard deviation (SD), median, minimum value and maximum value. The mean and median will be presented with one more decimal place than the original data; the standard deviation with two more decimal places than the original data; and minimum and maximum values with the same number of decimal places as the original data. Categorical variables will be summarized using frequency tables (number of patients and percentage of patients in each category). Unless otherwise stated, percentages will be calculated out of the analysis set total for the treatment group. Percentages will be rounded to one decimal place.

For log transformed data, the following descriptive statistics will be presented: n (number of patients with available data), geometric mean, geometric coefficient of variation (GCV%), geometric standard deviation factor (GSD), arithmetic mean, standard deviation, coefficient of variation (CV%), median, minimum and maximum value.

GCV (%) will be calculated as

$$100 \cdot \sqrt{(\exp(s^2) - 1)}$$

where s is the SD of the data on a log scale.

Individual data will be presented in patient listings. All patient data listings will be sorted by treatment and patient identifier ID. The first 3 digits of the patient ID denotes the center number and the next 4 digits denotes the individual patient number.

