4.2.6 Pharmacokinetic analyses

The PK analysis set is defined in Section [2.1.6](#).

The exclusion of any patients from the PK analysis will be agreed by the study physician, statistician and PK Scientist during the data review meeting (DRM). The exclusion of concentration data from the PK analysis for an individual time point will be documented by the PK Scientist including the reason(s) for exclusion. These individual concentration data will be listed.

Plasma exenatide concentrations will be listed.

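### Could the PK listing show first-dose 5 µg concentrations under a 10 µg heading, and should the SAP change because of it?

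*Protocol*

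**What the plan says.** **Sampling.** In Protocol Addendum (3), Pharmacokinetic Sampling: "Additional PK sampling will be performed at Visit 3 in a subset of subjects". Group A gives one sample 2 hours after the dose. For Group B, "PK samples will be collected twice during Visit 3: once at 30 minutes post dose and once at 4 hours post dose". The addendum's schedule has a single column, Visit 3, day 0. Up to two further samples per patient are allowed if the investigator and sponsor agree, with no set visit or time.

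**Dose at Visit 3.** Protocol 6.1 and 6.1.3, repeated in SAP 1.2, have both exenatide arms injecting 5 µg twice daily for about four weeks. The 10 µg arm steps up after Visit 5. The addendum changes when PK patients inject on the day of Visit 3 and drops the evening dose. It does not change the amount.

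**Presentation.** SAP 2.1.7, on the PK set: "Patients will be presented in accordance to the actual treatment received". SAP 4.1.1: "All patient data listings will be sorted by treatment and patient identifier ID". SAP 4.2.6: "Plasma exenatide concentrations will be listed". SAP 6 confirms that, for lack of data, concentrations are only listed.

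**Cross-reference.** SAP 4.2.6 begins "The PK analysis set is defined in Section" and then gives 2.1.6. That section reads "The safety follow-up (SFU) analysis set consists of all patients who have at least 1 safety follow-up period assessment". The PK set is in 2.1.7.

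**The concern.** SAP 2.1.7 speaks of patients, not samples, and a patient in the 10 µg arm who reaches the step-up receives both doses by design. The SAP's other use of the same idea is in the Safety set: "Patients will be analyzed and presented in accordance to the actual treatment received, regardless of planned treatment assignment". That section attaches one label to each patient. Its only rule for someone exposed to both doses, written for patients randomised to placebo, puts the whole patient under 10 µg.

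A programmer who borrowed that rule would list Visit 3 concentrations from the 10 µg arm under 10 µg, although each followed 5 µg. Two identical Visit 3 samples could also fall under different headings because one patient stepped up later and the other stopped before Visit 5. At stake is the reading of the listing: someone could take first-dose 5 µg concentrations for 10 µg exposure, or compare the two headings as if they were two doses.

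**Working it through.** **1. Reproduce the planned number.** From the addendum, Group A is 8 per arm and Group B is 4 per arm.

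- Patients: 3 × 8 + 3 × 4 = 24 + 12 = 36, or 12 per arm. This matches the addendum's minimum of 36.

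**2. Count scheduled samples.** Group A gives 1 sample per patient, Group B gives 2.

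- Per arm: 8 × 1 + 4 × 2 = 16.
- Two exenatide arms: 2 × 16 = 32, from 24 patients.

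**3. Attach the dose.** Sampling is on day 0. The step-up is at Week 4, that is 4 × 7 = day 28.

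- Scheduled exenatide samples after 5 µg: 32.
- Scheduled exenatide samples after 10 µg: 0.

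Only the discretionary extra samples could follow 10 µg. The documents do not say how many were drawn, so they are left out of the counts.

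**4. Compare the possible readings of SAP 2.1.7.**

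| Reading of treatment received | 10 µg-arm Visit 3 samples listed under | Is the heading wrong? |
|---|---|---|
| Dose injected before the sample | 5 µg | No |
| Regimen of the arm | 10 µg arm | No: that regimen starts at 5 µg |
| Highest dose ever received, borrowed from SAP 2.1.5 | 10 µg, if the patient stepped up | Yes, if read as the dose at sampling |

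Under the third reading, at most 16 of 32 scheduled samples (50%), from 12 patients, sit under 10 µg after a 5 µg injection. That maximum assumes that all 12 reached the step-up and that the planned minimum was enrolled. SAP 1.3 gives 122 randomised against 195 planned, and SAP 6 cites lack of data, so the true count is unknown.

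**5. Can the preceding dose be recovered?** Yes for scheduled samples. Before Visit 5 it is 5 µg in both exenatide arms, unless a dosing deviation was recorded; Protocol 8.8 requires deviations to be entered in the eCRF. The addendum requires the actual date and time of each sample. It does not mention the injection time, but the nominal times (30 minutes, 2 hours, 4 hours) are fixed by group.

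**6. What depends on the label?** SAP 1.1.3 makes PK exploratory. SAP 2.1.7, 4.2.6 and 6 provide a listing and nothing else: no summary by dose, no model, no test. Neither document states an aim of describing 10 µg exposure or comparing PK between doses. The number of results that change with the label is zero.

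**The case for a change.** The strongest case for a change is that it would cost little and the text is open. The PK rule is written for patients, and the only nearby precedent for a patient with both doses points to 10 µg. The data do not settle it unaided: in the study schedule, the eCRF item for the injected dose on the day before a visit is marked only at Visit 11 and at early discontinuation, so a programmer who looked there could find the later dose. With no PK summary planned, the heading carries more weight for a reader. The addendum's rationale also speaks of relating safety to maximum concentrations and recruits evenly by arm, which may invite a comparison of doses that these samples cannot support.

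Part of this stands. SAP 2.1.7 does leave the phrase undefined for a sample, and showing visit, nominal time and preceding dose beside each concentration is good listing practice. The rest does not carry the point. The both-doses rule in SAP 2.1.5 belongs to another analysis set and to placebo-randomised patients, so extending it to the 10 µg arm is inference. SAP 4.2.6 specifies no columns and no listing shells are in these documents, so visit and sampling time may already be planned. The population PK work named in the addendum is not part of the SAP, and such a model takes the dose and time of each record as input, not the heading of a listing.

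**Conclusion.** No change to the plan follows. The timing facts are firm: at the planned minimum, all 32 scheduled exenatide samples follow 5 µg and none follows 10 µg. The mislabelling is only possible. It needs one particular reading of SAP 2.1.7, and even then reaches at most 16 of the 32 samples in one exploratory listing.

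This is a gap in presentation detail that a PK programmer can fill sensibly from the titration text and the recorded deviations. Filling it in the SAP would alter no estimate, test or conclusion. The wrong section number in SAP 4.2.6 is clerical: the heading of 2.1.7 leaves no doubt which set is meant.

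The conclusion rests on PK remaining a listing, as SAP 6 states, and on the absence of any stated aim to compare PK between the two doses. If concentrations were later summarised by dose, the label would have to be settled first.
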